## **5.9 Integrated Correlative Studies**

### **5.9.1 Whole Exome Sequencing (WES)**

#### **5.9.1.1 Specimens Receipt and Processing at the EET Biobank**

Tumor tissue received in formalin will be paraffin-embedded. FFPE tissue blocks will be sectioned to generate an initial hematoxylin and eosin (H&E)-stained slide. All H&E stained slides will undergo a pathology QA review and annotation for macrodissection, if needed. Following macrodissection, tumor tissue from unstained slides will be scraped for co-extraction of DNA and RNA. The nucleic acids will be analyzed to determine concentration and quality. Aliquots of DNA will be shipped to the central sequencing laboratory for analysis.

DNA will be extracted from blood collected in cfDNA Streck tubes at baseline, following plasma processing. DNA will be quantitated, and then stored in a -80°C freezer until shipping for analysis.

#### **5.9.1.2 Site Performing Correlative Study**

This assay will be performed at the NCLN Genomics Laboratory under the supervision of [name].

## **5.10 Exploratory/Ancillary Correlative Studies**

### **5.10.1 RNA Sequencing**

#### **5.10.1.1 Specimens Receipt and Processing at the EET Biobank**

Tumor tissue received in formalin will be paraffin-embedded. FFPE tissue blocks will be sectioned to generate an initial hematoxylin and eosin (H&E)-stained slide. All H&E stained slides will undergo a pathology QA review and annotation for macrodissection, if needed. Following macrodissection, tumor tissue from unstained slides will be scraped for co-extraction of DNA and RNA. The nucleic acids will be analyzed to determine concentration and quality. Aliquots of RNA will be shipped to the central sequencing laboratory for analysis.

#### **5.10.1.2 Site Performing Correlative Study**

This assay will be performed at the NCLN Genomics Laboratory under the supervision of [name].

#### 5.10.2 Transcriptional Regulators

##### 5.10.2.1 Specimens Receipt and Processing at the EET Biobank

Following standard processing and paraffin embedding at the EET Biobank, tissue blocks will be stored at room temperature (not exceeding 25 degrees Celsius) until sectioning. At sectioning, five (5) 4 $\mu$ m tissue sections will be cut onto the center of sequentially numbered charged/plus slides (1 tissue section per slide) using a standard microtome. Slides will be dried overnight at room temperature. Five 4 $\mu$ m thick slides will be shipped to the [name] lab at MSKCC for transcription regulator analysis. Slides will have an inventory of relevant specimen IDs and the date of tissue sectioning. Date of tissue sectioning may be provided in the shipping manifest.

##### 5.10.2.2 Site Performing Correlative Study

This assay will be performed at the [name] Laboratory at the Memorial-Sloan Kettering Cancer Center, under the supervision of [name]., Ph.D.

Tissue on slides not utilized for an assay within 2 weeks of sectioning the tissue block will be stored in a closed container at -80 degrees Celsius in the [name] lab freezer.

The [name] lab will coordinate and prioritize subsequent studies to include multiplex tissue staining. The multiplex staining studies will involve a variety of relevant disease markers including (at a minimum) ASCL1, NeuroD1, Pou2F3, c-Myc, and Yap-1. Study relevant markers will be incorporated into several Vectra panels and supplemented with immune markers already validated to work in FFPE multiplex panels by the [name] lab who routinely perform these studies. Should desired, unvalidated markers prove technically problematic for multiplex staining, standard IHC will be used, slides will be scanned and digitally quantified using the Halo image analysis platform.

#### 5.10.3 Immune Cell Markers

##### 5.10.3.1 Specimens Receipt and Processing at the EET Biobank

Following standard processing and paraffin embedding at the EET Biobank, tissue blocks will be stored at room temperature (not exceeding 25 degrees Celsius) until sectioning. At sectioning, five (5) 4 $\mu$ m tissue sections will be cut onto the center of sequentially numbered charged/plus

slides (1 tissue section per slide) using a standard microtome. Slides will be dried overnight at room temperature. Five 4 $\mu$ m thick slides will be shipped to the [name] lab at UVA for Immune Cell Marker analysis. Slides will have an inventory of relevant specimen IDs and the date of tissue sectioning. Date of tissue sectioning may be provided in the shipping manifest.

#### 5.10.3.2 Site Performing Correlative Study

This assay will be performed at the [name] Laboratory at the University of Virginia, under the supervision of [name].

The [name] lab will coordinate and prioritize subsequent studies to include multiplex tissue staining. The multiplex staining studies will involve a variety of relevant immune markers including (at a minimum) PDL1, CD8, NK cells, regulatory and effector T-cells, arginase, and IDO. Study relevant markers will be incorporated into Vectra panels. Should desired, unvalidated markers prove technically problematic for multiplex staining, standard IHC will be used.

#### 5.10.3.3 Contact information for notification of specimen shipment

See Section 5.7.1.

#### 5.10.4 ctDNA

##### 5.10.4.1 Specimens Receipt and Processing at the EET Biobank

Whole blood collected in Streck tubes will be centrifuged to separate plasma. Following plasma processing, DNA will be processed from blood at baseline. At disease progression, plasma and buffy coat will be processed and stored. Plasma and buffy coat aliquots will be stored in a -80°C freezer.

##### 5.10.4.2 Site Performing Correlative Study

This assay will be performed at the NCLN Genomics Laboratory under the supervision of [name].

#### 5.10.5 Circulating Immune Cells

##### 5.10.5.1 Specimens Receipt and Processing at [name] Laboratory (MITS core)

Frozen PMBCs will be received by the [name] Laboratory samples will be processed for circulating immune cells using flow cytometry.

#### 5.10.5.2 Site Performing Correlative Study

This assay will be performed at the [name] Laboratory at the University of Virginia, under the supervision of [name].

#### 5.10.5.3 Contact information for notification of specimen shipment

See Section 5.7.1.

### 5.10.6 Immunogenicity

#### 5.10.6.1 Specimens Receipt and Processing at [name] Laboratory (MITS core)

PBMCs received by the [name] Laboratory will be processed for immunogenicity using ELIspot assays. The enzyme-linked immunospot (ELISpot) assay is a highly sensitive immunoassay that measures the frequency of cytokine-secreting cells at the single-cell level. In this assay, cells are cultured on a surface coated with a specific capture antibody in the presence or absence of stimuli.

#### 5.10.6.2 Site Performing Correlative Study

This assay will be performed at the [name] Laboratory at the University of Virginia, under the supervision of [name].

#### 5.10.6.3 Contact information for notification of specimen shipment

See Section 5.7.1.

### 5.10.7 Entinostat Pharmacokinetics

#### 5.10.7.1 Specimens Receipt and Processing at JHU APC

Plasma will be received by the JHU APC. Samples will be processed for entinostat concentrations using LC/MS/MS.

#### 5.10.7.2 Site Performing Correlative Study

This assay will be performed at the JHU APC, under the supervision of [name]., Ph.D.

#### 5.10.7.3 Contact information for notification of specimen shipment.

See Section 5.7.2.

NCI Protocol #: 10399  
Version Date: August 17, 2021

#### 5.10.8 Atezolizumab Pharmacokinetics

##### 5.10.8.1 Specimens Receipt and Processing at OSUCCC PhASR

Serum will be received by the OSU PhASR. Samples will be processed for atezolizumab concentrations using ELISA kits.

##### 5.10.8.2 Site Performing Correlative Study

This assay will be performed at the OSU PhASR, under the supervision of [name].

##### 5.10.8.3 Contact information for notification of specimen shipment

See Section 5.7.3

## 6. TREATMENT PLAN

### 6.1 Agent Administration

Treatment will be administered on an outpatient basis (inpatient is allowed if clinically indicated). Reported adverse events and potential risks are described in Section 10. Appropriate dose modifications are described in Section 7. No investigational or commercial agents or therapies other than those described below may be administered with the intent to treat the patient's malignancy.

Patients will receive up to 4 cycles of induction treatment followed by maintenance treatment for a total of 1 year of combined treatment (or 17 cycles). Patients who are unable to tolerate carboplatin and etoposide may discontinue induction and receive maintenance treatment for the remaining duration of treatment. Order of administration during induction should be according to institutional standard. Entinostat should be taken prior to administration of other agents.

On day 1, when patient receives additional therapy, entinostat will be administered prior to other chemotherapy or immunotherapy agents. On day 1 of induction cycles, Atezolizumab will be administered first, followed by carboplatin, and lastly etoposide. Time intervals between infusions are per institutional standards.

Dose Escalation Schedule								
Dose Level	Induction (Cycles 1-4)				Maintenance (Cycles 5-17)		Cycle Length	
	Dose				Dose			
	Carboplatin	Etoposide	Atezolizumab	Entinostat	Atezolizumab	Entinostat		
Level -1 (ME)	AUC 5 IV D1	100 mg/m  IV D1-3	1200 mg IV D1	None	1200 mg IV D1	5 mg PO D1, 8, 15	21 days	
Level 1*	AUC 5 IV D1	100 mg/m  IV D1-3	1200 mg IV D1	2 mg PO D1, 8, 15	1200 mg IV D1	5 mg PO D1, 8, 15	21 days	
Level 2	AUC 5 IV D1	100 mg/m  IV D1-3	1200 mg IV D1	3 mg PO D1, 8, 15	1200 mg IV D1	5 mg PO D1, 8, 15	21 days	
Level 3	AUC 5 IV D1	100 mg/m  IV D1-3	1200 mg IV D1	5 mg PO D1, 8, 15	1200 mg IV D1	5 mg PO D1, 8, 15	21 days	

\*Starting Dose Level.

IV = intravenous, AUC = Area Under Curve, PO = Orally, ME = Maintenance entinostat.

Regimen Description – Induction (up to 4 cycles) #					
Agent	Premedication; Precautions*	Dose	Route	Schedule	Cycle Length
Entinostat	Take on an empty stomach (at least 1 hour before and 2 hours after a meal)	Assigned dose level	PO	Day 1, 8, 15	21 days (3 weeks)
Atezolizumab		1200 mg	IV infusion over 60 ( $\pm 15$ ) minutes**	Day 1	
Carboplatin	Dexamethasone NK1 antagonist 5-HT3 antagonist.	AUC 5***	IV infusion over 30-60 minutes	Day 1	
Etoposide		100 mg/m 	IV infusion over 60 (+/- 15) minutes	Days 1-3	

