## 5. BIOMARKER, CORRELATIVE, AND SPECIAL STUDIES

### 5.1 Summary Table for Specimen Collection

Time Point	Specimen	Send Specimens To:
Archival		
	
 
Formalin-fixed paraffin-embedded (FFPE) tumor tissue block (preferred) (mandatory)
 
 
If archival tissue block is not available, then submit:
 
 
20-25 (10-micron) unstained uncharged slides (mandatory)
 
10 (4-micron) unstained charged slides (optional)
 
	EET Biobank
Baseline (if archival tissue is unavailable)		
	
 
2-3 tissue cores in formalin (mandatory)
 
	EET Biobank
Cycle 1 Day 1		
	
 
Pre-treatment: 2 x 10 mL whole blood in Streck cfDNA tubes (mandatory)
 
	EET Biobank
	
 
Pre-treatment: 6 x 10 mL whole blood in sodium heparin (green top) tubes processed for flow cytometry and ELISpot, then frozen (mandatory)
 
	[name] Laboratory (MITS core)
Atezolizumab PK 	
 
Pre-dose: 1 x 6 mL whole blood in red-top (e.g. BD 367815 or 368660) tubes (mandatory)
 
After the end of the atezolizumab infusion at the same time as the ~2 hours post entinostat PK: 1 x 6 whole blood in red-top (e.g. BD 367815 or 368660) tubes (mandatory)
 
	OSUCCC PhASR
Entinostat PK 	
 
Pre-dose: 1 x 4 mL whole blood in sodium heparin (green top; e.g. BD 367871 or 367884) tubes (mandatory)
 
~0.5 hours post dose: 1 x 4 mL whole blood in sodium heparin (green top; e.g. BD 367871 or
 
	JHU APC

	
 
367884) tubes (mandatory)
 
• ~2 hours post dose: 1 × 4 mL whole blood in sodium heparin (green top; e.g. BD 367871 or 367884) tubes (mandatory)
 
	
Cycle 1 Day 2		
Entinostat PK 	
 
Prior to etoposide-dose: 1 × 4 mL whole blood in sodium heparin (green top; e.g. BD 367871 or 367884) tubes (mandatory)
 
	JHU APC
Cycle 1 Day 8		
Entinostat PK 	
 
Pre-dose: 1 × 4 mL whole blood in sodium heparin (green top; e.g. BD 367871 or 367884) tubes (mandatory)
 
	JHU APC
Cycle 1 Day 15		

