Entinostat PK 	
 
Pre-dose: 1 × 4 mL whole blood in sodium heparin (green top; e.g. BD 367871 or 367884) tubes (mandatory)
 
	JHU APC
Cycle 2 Day 1		
	
 
Pre-treatment: 6 × 10 mL whole blood in sodium heparin (green top) tubes processed for flow cytometry and ELISpot, then frozen (mandatory)
 
	[name] Laboratory (MITS core)
Atezolizumab PK 	
 
Pre-dose: 1 x 6 mL whole blood in red-top (e.g. BD 367815 or 368660) tubes (mandatory)
 
After the end of the atezolizumab infusion at the same time as the ~2 hours post entinostat PK: 1 x 6 mL whole blood in red-top (e.g. BD 367815 or 368660) tubes (mandatory)
 
	OSUCCC PhASR
Entinostat PK 	
 
Pre-dose: 1 × 4 mL whole blood in sodium heparin (green top; e.g. BD 367871 or 367884) tubes (mandatory)
 
• ~0.5 hours post dose: 1 × 4 mL whole blood in sodium heparin (green top; e.g. BD 367871 or 367884) tubes (mandatory)
 
• ~2 hours post dose: 1 × 4 mL whole blood in sodium heparin (green top;
 
	JHU APC

	e.g. BD 367871 or 367884) tubes (mandatory)	
Cycle 2 Day 2		
Entinostat PK 	
 
Prior to etoposide-dose: 1 x 4 mL whole blood in sodium heparin (green top; e.g. BD 367871 or 367884) tubes (mandatory)
 
	JHU APC
Cycle 3 Day 1		
	
 
Pre-treatment: 6 x 10 mL whole blood in sodium heparin (green top) tubes processed for flow cytometry and ELISpot, then frozen (mandatory)
 
	[name] Laboratory (MITS core)
Atezolizumab PK 	
 
Pre-dose: 1 x 6 mL whole blood in red-top (e.g. BD 367815 or 368660) tubes (mandatory)
 
~0.5 hours after the end of the infusion: 1 x 6 mL whole blood in red-top (e.g. BD 367815 or 368660) tubes (mandatory)
 
	OSUCCC PhASR
Cycle 4 Day 1		
	
 
Pre-treatment: 6 x 10 mL whole blood in sodium heparin (green top) tubes processed for flow cytometry and ELISpot, then frozen (mandatory)
 
	[name] Laboratory (MITS core)

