### 6.1.4 Etoposide

Etoposide will be administered at a dose of 100 mg/m^2 IV over 60 minutes on Days 1-3 of each cycle. Preparation of each agent, administration instructions, and order of infusions should follow institutional policy.

Etoposide dose rounding is allowed as per institutional guidelines.

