
e: Tumor measurements are repeated every 6 weeks (+/- 1 week) for year 1.
 
f: Tumor measurements are repeated every 3 months (+/- 2 weeks) for year 2, then every 6 months (+/- 1 month) thereafter. Documentation (radiologic) must be provided for patients removed from study for progressive disease.
 
g: CT Chest/Abd/Pelvis are performed within 4 weeks of study registration and then every 6 weeks(+/- 1 week) for year 1, every 3 months (+/- 2 weeks) for year 2, then every 6 months (+/- 1 month) thereafter until progression. Patients who discontinue study treatment for reasons other than disease progression will continue radiographic evaluations per this schedule during Follow-Up until disease progression is documented. For pts with untreated brain mets, brain MRI is performed within 4 weeks of study enrollment and then subsequently at same schedule as CT imaging; otherwise as clinically indicated.
 
h: If participant is no longer coming to the study site, study staff will call or email the participant to check overall survival every 3 months for years 1-2, then every 6 months (+/- 1 month) until 5 years from registration.
 
i: Day 1 of every even cycle.
 
j: May continue per investigator/patient discretion as standard of care. Labs, vitals, performance status should be done as routine standard of care and are not indicated on this table. End of treatment visit may occur on a day when standard of care atezolizumab is administered or a separate day.
 
k: Tumor biopsy (optional), blood collection in cfDNA Streck tube for ctDNA, Flow cytometry, and ELispot are to be performed at the time of progression. Refer to Sections 5.1 and 5.5.
 
l: Entinostat PK on Cycles 1-2, Day 1: prior to entinostat, ~0.5 hr post dose, and ~2 hrs post dose; Cycles 1-2, Day 2: prior to etoposide infusion; Cycle 1, Day 8 and 15: prior to entinostat.
 
m: Atezolizumab PK on Day 1 of Cycles 1 and 2: prior to atezolizumab and after the end of the atezolizumab infusion at the same time as the ~2 hr post entinostat PK. On Day 1 of Cycles 3, 4, 6, and 8: prior to atezolizumab and ~0.5 hr after completion of atezolizumab infusion.
 
n: Free or total T3/T4 may be performed per institutional standards.
										

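### The Cycle 1 and 2 post-infusion atezolizumab sample is timed to an entinostat dose that some patients will not receive and depends on an infusion order the plan states inconsistently (minor)

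*Combined protocol and SAP*

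**What the plan says.** **Infusion order.** Section 6.1 first says "Order of administration during induction should be according to institutional standard". Its next paragraph says "On day 1 of induction cycles, Atezolizumab will be administered first, followed by carboplatin, and lastly etoposide". Section 6.1.4 then says that "order of infusions should follow institutional policy". Section 6.1 also puts entinostat before every infusion and leaves the intervals between infusions to the institution.

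**Sample time, Cycles 1 and 2.** Section 5.1 makes a post-dose atezolizumab sample mandatory on Day 1 of both cycles, to be taken "After the end of the atezolizumab infusion at the same time as the ~2 hours post entinostat PK". The atezolizumab row of Section 5.8 has the same rule, and footnote m of the Section 11 calendar reads "prior to atezolizumab and after the end of the atezolizumab infusion at the same time as the ~2 hr post entinostat PK". No tolerance around 2 hours is given.

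**Sample time, Cycles 3, 4, 6 and 8.** Here the sample is due about "0.5 hours after the end of the infusion", with no reference to entinostat.

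**Use of the data.** Exploratory objective 1.3.6 relates baseline atezolizumab clearance to overall survival. Section 2.5.9 defines that quantity as clearance of the first dose, and Section 9.3 estimates clearance by mixed-effects pharmacokinetic modelling with a time-varying component.

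**The concern.** The Cycle 1 and 2 rule sets two conditions at once: the infusion is over, and it is about 2 hours since entinostat. Whether both can hold depends on the order of infusions, which the plan does not settle, and on entinostat being given at all, which the plan does not guarantee.

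Where the conditions conflict, sites must improvise. One may draw at 2 hours while atezolizumab is still running, another may wait for the end of infusion, a third may skip the sample. The Cycle 1 Day 1 sample is the only post-dose atezolizumab sample before the Cycle 2 trough. A sample drawn mid-infusion but recorded as post-infusion would be wrong rather than merely imprecise, and the pattern of such errors would follow site practice and dose level.

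**Working it through.** **1. Is the order statement truly contradictory?** Carboplatin and atezolizumab are given on day 1 only, and etoposide is the sole infusion on days 2 and 3. A rule about infusion order during induction can therefore concern only day 1, the day for which Section 6.1 fixes the order. The statements cover the same case and disagree.

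**2. Patients with no entinostat.** The dose table in Section 6.1 shows none in induction at Level -1, so the 2-hour time does not exist there on either sampling day, whatever the order. Sections 7.2.1 and 7.2.3 also allow entinostat to be stopped, or held for an event attributed to it alone, while the other drugs continue; the same gap can then arise on Cycle 2 Day 1. The footnotes to Section 5.1 say what to do when etoposide is held, but not when entinostat is absent.

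**3. Timeline when entinostat is given.** Inputs in minutes: carboplatin 30–60 and etoposide 60 ± 15, so 45–75 (Section 6.1 regimen table); atezolizumab 60 ± 15, so 45–75, for the first dose, and 30 ± 10, so 20–40, for the second if the first was tolerated (Section 6.1.2). Time zero is the entinostat dose. Infusions are assumed to start at once, which is the most favourable case. Gaps are not stated; g minutes before each infusion is an assumption.

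End of atezolizumab = sum of infusion times up to and including atezolizumab + g × number of those infusions.

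- *Atezolizumab first, Cycle 1:* 45–75 with no gaps and 75–105 with g = 30. The plan's 120-minute target is attainable.
- *Carboplatin and etoposide first, Cycle 1:* 30 + 45 + 45 = 120 to 60 + 75 + 75 = 210, mid-range 45 + 60 + 60 = 165.
- *Same order, Cycle 2:* 30 + 45 + 20 = 95 to 60 + 75 + 40 = 175, mid-range 135.
- *Carboplatin only first:* 30 + 45 = 75 to 60 + 75 = 135 in Cycle 1; 30 + 20 = 50 to 60 + 40 = 100 in Cycle 2.

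The table gives the chance that atezolizumab has ended by 120, 135 and 150 minutes, assuming times uniform within their limits (200,000 draws).

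| Given before atezolizumab | Cycle | g = 0 | g = 10 |
|---|---|---|---|
| Carboplatin and etoposide | 1 | 0%, 2%, 17% | 0%, 0%, 0% |
| Carboplatin and etoposide | 2 | 14%, 50%, 86% | 0%, 1%, 14% |
| Carboplatin only | 1 | 88%, 100%, 100% | 35%, 78%, 99% |
| Carboplatin only | 2 | 100%, 100%, 100% | 100%, 100%, 100% |

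Hand check of the first row: three uniform times of width 30 give 15³/(6 × 30³) = 2% by 135 minutes and 30³/(6 × 30³) = 17% by 150. With g = 30 and carboplatin only first, the chance by 120 minutes falls to 0% in Cycle 1 and 8% in Cycle 2.

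With both chemotherapy drugs first at mid-range times, atezolizumab starts at 45 + 60 = 105 minutes. A Cycle 1 draw at 120 minutes would follow 15/60 = 25% of the dose.

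**4. Effect on baseline clearance.** The documents give no pharmacokinetic parameters, so these are assumptions: one compartment, volume 6 L, half-life 10, 20 or 30 days; between-patient SD 30% for clearance and 20% for volume; clearance declining by 0.15 on the log scale (SD 0.2, time constant 40 days); residual error 15% or 25%.

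- A draw 1 hour late, after the infusion, changes concentration by 1 − 2^(−1/(24 × half-life)): 0.29%, 0.14% and 0.10% respectively.
- The SD of a patient's log first-dose clearance is the square root of the clearance element of (JᵀJ/σ² + prior precision)⁻¹, where J holds the sensitivities of log concentration to the parameters and σ is the residual error. Losing both the Cycle 1 and Cycle 2 post-infusion samples raises it by 0.1 to 0.5 percentage points when all later cycles are sampled (for example 12.1% to 12.2% at 20 days and 15% error), and by 0.3 to 1.2 points when sampling stops at Cycle 2 Day 1.

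**The case against.** The day-1 sentence is the more specific one, and a site that follows it finishes atezolizumab at 45–75 minutes and has no difficulty. The share of sites that would give chemotherapy first is not known. Every sampling passage says the draw comes after the infusion, so a mid-infusion draw would be a deviation, and at Level -1 that half of the rule still applies. Section 5.5.3.4.1 requires the exact collection time on the label, and Section 9.3 uses a model that can take actual times. Combining two draws is a reasonable way to limit sampling. The objective is exploratory, and no dose decision, safety rule, or primary or secondary endpoint uses this sample.

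Most of this stands, and it limits the point. It does not remove it. Two other sentences support a site that uses its own order. Reading the day-1 sentence as binding does not help a patient who has had no entinostat. The sampling sections ask for the draw time but do not expressly ask for infusion start and stop times, which are needed to recognise a sample drawn too early.

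A reader might infer that the rule works only with atezolizumab first. That fails when carboplatin alone precedes it and gaps are short. A reader might also take the 5.6% to 41.3% of patients treated at Level -1 in the Section 9.1.3 simulations as the share of unusable samples. Those figures are simulated allocations; they show how many patients could lack a defined sampling time, not how many samples would be lost.

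**Conclusion.** The point holds as a minor defect. The order statements conflict. The sampling time is undefined at Level -1, and on Cycle 2 Day 1 when entinostat is absent and the other drugs continue. It is normally unattainable in Cycle 1 if both chemotherapy drugs precede atezolizumab: the earliest possible end is exactly 120 minutes, with every infusion at its lower limit and no gaps. For Cycle 2, or with carboplatin alone first, the answer turns on gaps and on how loosely 2 hours is read, and the plan states neither.

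The consequence is a risk of mistimed, missing or site-dependent samples for objective 1.3.6. The stronger inference, that baseline clearance would be materially less precise, is not supported: under the assumed pharmacokinetics the loss is small even with both samples missing, and smaller still for a late sample with its true time recorded. That calculation does not cover a mid-infusion sample coded as post-infusion, which is the case most worth preventing. The timeline uses the plan's own infusion limits; the percentages rest on uniform times and assumed gaps.

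**What to change.** - In Section 5.1, the atezolizumab row of Section 5.8, and footnote m of Section 11, define the Cycle 1 and Cycle 2 post-dose atezolizumab sample as about 0.5 hours after the end of the atezolizumab infusion, as for Cycles 3 to 8. This works under any order and at every dose level.
- Keep the 2-hour entinostat sample separate. Allow one shared draw when the two times coincide, and say how close counts as coinciding.
- Record actual infusion start and stop times with each draw time.
- Reconcile the order statements in Sections 6.1 and 6.1.4. Which order applies is for the sponsor to decide.

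In Cycle 1 with no gaps, the re-timed sample falls 45 + 30 = 75 to 75 + 30 = 105 minutes after entinostat with atezolizumab first, and 120 + 30 = 150 to 210 + 30 = 240 minutes with both chemotherapy drugs first. The draws will therefore often not coincide. The cost is wording in three places and at most one extra draw time for a 6 mL sample on two days; the number of samples does not change.
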